- Patients who provide voluntary consent to participate in the study (Annex 2). If the participant is not in full physical or intellectual capacity to provide their signature in the informed consent, the responsible investigator will seek consent from their direct family member or the legally designated person to make decisions on their behalf regarding health matters. This measure is adopted to ensure the participant's rights are respected and the integrity of the consent process is maintained, even in situations where their decision-making capacity may be compromised.

Exclusion Criteria:

Patients from whom information from the thermal imaging camera cannot be obtained due to technical reasons.

Sample Size:

To determine the degree of concordance between the temperature recorded by the thermal camera and axillary temperature, a minimum of 224 pairs of data (224 temperature records by thermal camera vs. 224 axillary temperature records) will be required to estimate an Intraclass

Correlation Coefficient (expected to be 0.8 or higher) with an estimation error of +- 0.05 points, a confidence level of 95%, and anticipating a 10% loss.

Data Collection:

Temperature measurements will be autonomously recorded by the SF-HANDHELD-80TA05 thermal imaging camera, or another with similar characteristics, which provides temperature values every second, thermal images, bed number, date, and time.

The rest of the variables needed for the study will be manually collected by the researchers or through the clinical information system (CIS) "Innovian" and included in a study-dedicated database hosted on the hospital intranet.

Finally, all data will be collected in a pseudonymized manner. For this purpose, two databases will be constructed. One will contain personal data associated with a code (one for each patient), which will be safeguarded by the investigator. The second database will contain the associated clinical data. In the case of images generated by thermal cameras, these will also be pseudonymized, generating images with the aforementioned association code. These coded images will be sent to the Computing Center of the European University of Madrid for the creation of temperature patterns (secondary objectives 4 and 5) and for the adequacy of regional thermal measurement (secondary objective 6).

Standard Practice in Peripheral Temperature Measurement in Our Unit

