The standard practice for peripheral temperature measurement in the ICU at HLA Moncloa University Hospital is not formally documented but adheres to recommendations for monitoring temperature in critically ill patients. Peripheral temperature is obtained using a contact thermometer in the axilla every 8 hours or whenever thermal disturbances are suspected by healthcare personnel (both medical and nursing staff).

Axillary temperature measurement through standard practice will be repeated every 8 hours and collected in triplicate to establish an average used for assessing concordance at that point and so forth until reaching the 224 measurements needed to complete the primary objective of the study. If, during the 8-hour collection, there is a difference of more than 15% between the first 3 measurements, a fourth measurement will be taken, and only the average of the three most similar measurements will be used for concordance. If all four measurements are different, a fifth measurement will be taken, and so on until three measurements considered similar are obtained.

Definitions of Thermal Disturbances and Infectious Complications:

- Fever: Defined as a central temperature (rectal, esophageal, vesical, or tympanic) $\geq 38.3^{\circ}\text{C}$. Peripheral temperature (cutaneous or axillary) is 0.6 to 1°C lower than central temperature; therefore, for this study, we will consider a peripheral temperature $\geq 37.5^{\circ}\text{C}$ as a fever.
- Hypothermia: Defined as a central temperature $< 35^{\circ}\text{C}$ or peripheral temperature $< 34.2^{\circ}\text{C}$.
- Infectious Complications: Will include both patients admitted to the ICU due to an infection (pre-admission infection) and patients who develop an infection during their stay in the ICU (infection during admission). Identification and diagnosis of either type of infection will be

carried out by the attending physician following established clinical practice recommendations and guidelines in each specific case. The task of the researchers will be limited to reviewing the patient's medical history and collecting data.

Temporal Differences in Fever Detection:

The time of fever detection will be identified for each measurement method (standard practice vs. thermal imaging camera), and the temporal difference in minutes between them will be determined.

Creation of Temperature Patterns:

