the server dedicated to the study, located physically within the ICU and connected only to the hospital intranet. This ensures that the information collected for the study has the same level of security as other information related to hospitalized patients. Additionally, all records made on the server will be pseudonymized from personal information. Identifying a person through the thermal image is not possible without additional information; thus, for all intents and purposes, it is considered anonymized information.

[figure not shown]

Figure 1. Example of Thermal Image

5. Temperature data for each patient included in the study can be accessed through a tablet connected only to the hospital intranet and will remain within the ICU.
6. At the time of discharge or patient exitus, the principal investigator will review the patient's medical history to create a pseudonymized database that records study variables and patient temperature data.
7. Once data collection is complete over the 11-month study period, the principal investigator will physically send pseudonymized temperature data and thermal images to the Computing Center of the European University of Madrid, which is committed to maintaining data confidentiality and destroying any possible copies of the material once study objectives are fulfilled.
8. After completing the study, pseudonymized patient data will remain recorded for 5 years on the server physically located within the ICU. This is in case data consultation is necessary for clinical reasons or regarding the publication of study data.

Variables

Primary:

- Axillary Temperature
- Temperature from Thermal Imaging Camera

Secondary:

- Age
- Gender
- Reason for Admission:
 - Altered Level of Consciousness and Other Neurological Disorders
 - Acute Coronary Syndrome
 - Cardiac Arrhythmias
 - Cardiorespiratory Arrest
 - Heart Failure/Cardiogenic Shock

- Hypovolemic Shock
- Sepsis/Septic Shock
- Shock of Other Etiology
- Respiratory Failure
- Renal Failure and Metabolic Disorders
- Intoxications
- Head Trauma
- Other Traumas without Head Injury
- Postoperative Monitoring and Surveillance
- Monitoring and Surveillance of Non-Surgical Procedures
- Other Unspecified Medical or Surgical Conditions
- Hypertension (Yes/No)
- Diabetes Mellitus (Yes/No)
- Dyslipidemia (Yes/No)
- SAPS3 at Admission
- Thermal Image
- Fever (Yes/No)
- Hypothermia (Yes/No)
- Infectious Complications (Pre-existing or During Admission) Date and Time

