All information obtained will be pseudonymized before leaving the hospital network, ensuring the identification of any individual through this information is not possible. The transfer of information to the Computing Center of the European University of Madrid will be done physically on a hard drive guarded by the researchers and deposited at the hospital facilities after the study's completion. Researchers at the Computing Center of the European University of Madrid also commit to the strictest confidentiality in accessing, collecting, and processing data, even though they will always be pseudonymized, and commit to strict compliance with current legislation: Law 41/2002.

Cronograma

	November 2023	November 2023	December - January 2024	May 2024	October 2024	November 2024
Protocol Study Drafting						
HLA Moncloa Hospital Permissions						
Presentation to CEIm (Ethics Committee)						
CEIm (Ethics Committee) validation						
Purchase and Installation of Equipment in ICU						
Patient Recruitment						
Interim Report						
Statistical Analysis						
Final Report"						
Article Writing and Commencement of Outreach						

Economic Report

Budget	
Concept	Grant Awarded *
Equipment	3200€
Consumable Material	200€
Publication Expenses	600€
Total	4000€

*** Grant Awarded corresponds to the RESEARCH GROUPS JOINT GRANTS CALL 2023. ASISA FOUNDATION-UNIVERSIDAD EUROPEA DE MADRID CHAIR**

Budget Justification

At the beginning of the project, €1,200 will be used to purchase 3 high-quality thermal cameras, valued at approximately €400 each. Additionally, a budget of €800 will be allocated for the purchase of a PC (€600) and consumable materials (€200) for interconnection and automation of image downloads.

After 6 months, another €1,200 will be used to complete the purchase of an additional 3 thermal cameras, along with a Tablet (€200) for data representation. Furthermore, €600 will be allocated for publication expenses, which may include article translation, publication fees, or dissemination of results at national and international conferences."

Bibliography

1. Chamorro C, Romera MA, Balandin B. Fever in critically ill patients. *Crit Care Med.* 36. United States2008. p. 3129-30; author reply 30.

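### The triplicate concordance series ends at 224 measurements, so the primary ICC will probably rest on the first three cameras and the early part of the 11 months, with no pairs required from the three cameras bought later

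*Protocol*

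**What the plan says.** Protocol, Sample Size: "a minimum of 224 pairs of data (224 temperature records by thermal camera vs. 224 axillary temperature records) will be required" to estimate the intraclass correlation coefficient, which is expected to be at least 0.8, "with an estimation error of +- 0.05 points, a confidence level of 95"%, and "anticipating a 10% loss".

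Protocol, Standard Practice in Peripheral Temperature Measurement in Our Unit: the axillary reading is taken in triplicate every 8 hours and averaged into one concordance value, and "so forth until reaching the 224 measurements needed to complete the primary objective of the study". The same section describes routine axillary measurement, every 8 hours or on suspicion of a thermal disturbance, with no end point.

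Protocol, Budget Justification: three cameras are bought at the beginning of the project. "After 6 months, another €1,200 will be used to complete the purchase of an additional 3 thermal cameras".

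Protocol, Data Collection: "Temperature measurements will be autonomously recorded by the SF-HANDHELD-80TA05 thermal imaging camera, or another with similar characteristics".

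Protocol, Interventions and Procedures, item 7, on sending the data out: "Once data collection is complete over the 11-month study period".

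No section asks for a number of pairs per camera, a spread of pairs over the period, or concordance pairs from the second batch. Neither the fever-timing comparison (Objective 3) nor the thermal curves (Objectives 4 and 5) are limited to the first three cameras.

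**The concern.** Two parts of the protocol interact. One is a stopping count for the primary reference measurement that runs from the start of recruitment. The other is a camera fleet that doubles partway through. If the count is reached before the second batch is installed, the primary ICC comes from half the devices, three rooms and an early stretch of the calendar, yet it will be read as the concordance of thermal cameras in this ICU.

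Room matters as well as device. The section on adequacy of regional measurement says that the camera takes the hottest point in the whole scene and may pick up staff or equipment. Error can therefore depend on the room and the installation even if all six cameras are identical. An offset specific to a later camera or room would not show in the primary estimate, while that camera's readings would still enter the fever times and thermal curves. Triplicate pairs that were not taken cannot be recovered at analysis.

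**Working it through.** **The plan's own figure.** The inputs from Sample Size are ICC ρ = 0.8, half-width 0.05 (full width w = 0.10), 95% confidence (z = 1.96), 10% loss and k = 2 methods. The Bonett formula for the width of an ICC interval is

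n = 8z²(1 − ρ)²(1 + (k − 1)ρ)² / (k(k − 1)w²) + 1

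This gives 8 × 3.8415 × 0.04 × 3.24 / (2 × 0.01) + 1 = 200.14, rounded up to 201. Then 201 / 0.9 = 223.3, rounded up to 224. The stated 224 is reproduced. The formula treats pairs as independent; whether they are is a separate question.

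**Time to reach 224.** Three cameras × 3 slots a day = 9 possible pairs a day (one bed per camera, assumed). Yield is the share of slots that give a usable pair from a consenting patient. The documents do not state it. Days = 224 / (9 × yield):

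- 100%: 24.9 days
- 75%: 33 days
- 50%: 50 days
- 25%: 100 days

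**Yield at which the series lasts until the second batch.** The gap runs from the start of recruitment to installation of cameras 4 to 6. Threshold = 224 / (9 × gap in days):

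- 6 months (182 days): 224 / 1,638 = 14%
- 4 months (121 days): 224 / 1,089 = 21%
- 3 months (91 days): 224 / 819 = 27%

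At any higher yield the set is full before those cameras exist.

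**A yield implied by the protocol's own targets.** Objective 4 lists 16 categories with at least 20 patients each, so 16 × 20 = 320 patients if each counts once. The curves cover 24 hours, so take at least one camera day per patient. Over 11 months (334 days) the first three cameras give 3 × 334 = 1,002 bed-days. The later three add:

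- 6-month gap: 3 × 152 = 456, total 1,458
- 4-month gap: 3 × 213 = 639, total 1,641
- 3-month gap: 3 × 243 = 729, total 1,731

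At one day per patient the implied occupancy by enrolled patients is 320 / 1,458 = 22%, 320 / 1,641 = 19.5% and 320 / 1,731 = 18%. The first exceeds its 14% threshold, the second is just under 21%, and the third is below 27%. At an assumed two days per patient the figures are 44%, 39% and 37%, all above their thresholds. This takes enrolment as even over time and every slot on an enrolled day as usable.

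**Share of camera time without required pairs.** With equal occupancy, cameras 4 to 6 supply 456 / 1,458 = 31%, 639 / 1,641 = 39% or 729 / 1,731 = 42% of camera bed-days.

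**What a per-camera ICC could show.** 224 / 6 is about 37 pairs. Turning the formula round, half-width = ½√[8 × 3.8415 × 0.04 × 3.24 / (2 × 36)] = ½ × 0.235 = 0.12, against the planned 0.05.

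**The case against.** A reader might infer that the later cameras are never compared with the axilla. The documents do not support that. Routine axillary readings have no stated end, and camera values are stored every second with bed, date and time. Objective 2 sets the camera against axillary thresholds and Objective 3 against routine practice, neither with a 224-pair limit. What the later cameras may lack is the triplicate-averaged reference behind the primary ICC. This objection stands and narrows the point.

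A reader might also take 25 days as the expected duration. It is a lower bound: every camera bed always occupied by a consenting patient and every triplicate usable.

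The gap before the second batch is not fixed either. The 6 months run from the beginning of the project, not from first enrolment, and the timeline's shading is not available. A shorter gap raises the threshold, which is why a range is given.

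A different model, or drift over time, is possible but not shown. The allowance for a similar camera applies equally to the first batch, and both batches cost the same €1,200. The case for covering all cameras does not need a model change, because room and installation can matter on their own.

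Finally, Sample Size calls 224 a minimum, so collection could run on. That is a fair reading of that section, but the measurement section ends the series on reaching 224. The two need reconciling. An analysis plan that is not shown might add results by camera, but it could not supply triplicate pairs that were never collected.

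**Conclusion.** The point holds in limited form. As written, the protocol lets the primary concordance set be filled on the first three cameras and rooms, early in the 11 months, and does not require the other three to contribute. That outcome is probable: avoiding it needs a yield of about 14% or less for a 6-month gap, 21% for 4 months or 27% for 3 months. Meeting Objective 4's patient targets with stays of about two days implies more than any of these. With one-day stays it exceeds the threshold only at the 6-month gap.

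The conclusion rests on one bed per camera, an assumed gap of 3 to 6 months and an assumed yield. It does not say that the 224 is miscalculated, that the later cameras go unchecked, or that they differ from the first. It says that the primary ICC may not represent devices and rooms that supply roughly 31% to 42% of camera bed-days under these assumptions.

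**What to change.** In the section on standard practice, replace the stopping phrase with a sampling schedule. Keep the total at about 224 pairs, spread the 8-hourly slots over the recruitment period, and reserve a share for each camera from its installation. An even split is about 37 pairs each (four cameras at 37 and two at 38 make 224). Cameras 4 to 6 can only be sampled once they are in place. Align the wording with Sample Size so that both sections say whether 224 is a minimum or the end of collection.

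Keep the pooled ICC as the primary result. Add the mean camera-minus-axilla difference by camera as a descriptive check. Do not rely on an ICC by camera, since about 37 pairs give a half-width of about 0.12.

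The cost is a change of wording and a sampling calendar, with about the same number of triplicate readings. The downside is that the primary result comes at the end of recruitment. The change has to be made before the 224 are used up.

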Body temperature is one of the most frequently studied physiological variables in hospitalized patients. The normal temperature value is around 36.7°C, with significant variability ranging from 35.3 to 37.7°C among different individuals or within the same person throughout the day. The definition of fever is established by a consensus reached by the American College of Critical Care Medicine and the IDSA, placing it at a central temperature of 38.3°C (1), where central temperature refers to the temperature of internal organs. This thermal elevation is typically found in approximately 50% of critical patients (2) and is not only clearly associated with infectious processes but can also be observed in various other conditions such as autoimmune diseases, oncological conditions, bleeding, inflammatory reactions, after surgical procedures, or drug-induced (3).

There are multiple methods for temperature measurement in Intensive Care Units (ICUs), with the most common being peripheral temperature measurement every eight hours using contact thermometers in the axilla(4). In patients with sustained fever or those undergoing therapeutic hypothermia, continuous monitoring of central temperature through rectal, tympanic, vesical, or esophageal methods can be performed (5). However, it is considered a more invasive measure, and its use is limited mainly due to technical difficulties, higher economic costs, and potential serious complications (6, 7).

Thermal monitoring in critical patients is essential. Many critical patients with fever will receive antibiotic treatment, even in the absence of evidence of infection, as early initiation of this treatment in septic patients clearly improves survival (8, 9).

The wide variability of temperature between individuals, circadian changes, different methods of temperature measurement, the influence of medications, and deficiencies in measurement methods make defining fever with a single temperature value impractical (10) Therefore, other patient variables should also be considered before establishing the presence of fever. One of these variables is the thermal curve, or the evolution of temperature throughout the day, which can be sustained or in peaks and may or may not respond to antipyretics, antibiotics, or other temperature control methods. Studying a patient's thermal curve is useful even before reaching definitive fever values (11).

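### The 15% trigger for a repeat axillary reading equals about 5.5°C, so it cannot screen the comparator for the primary ICC

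*Protocol*

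**What the plan says.** The rule is in the protocol under Standard Practice in Peripheral Temperature Measurement in Our Unit. Every 8 hours the axillary temperature is "collected in triplicate to establish an average used for assessing concordance at that point". If "there is a difference of more than 15% between the first 3 measurements, a fourth measurement will be taken", and then "only the average of the three most similar measurements will be used for concordance". A further step applies once four readings exist: "If all four measurements are different, a fifth measurement will be taken, and so on until three measurements considered similar are obtained". The base of the percentage is not stated, and the words *different* and *similar* have no number attached.

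The primary analysis, in the protocol's Statistical Analysis Plan section, is the ICC between camera and axillary temperature. The Sample Size section states its target for the ICC as "Correlation Coefficient (expected to be 0.8 or higher) with an estimation error of +- 0.05 points".

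The protocol also gives its own scale for judging a temperature difference. The opening background states "The normal temperature value is around 36.7°C". It goes on to describe "significant variability ranging from 35.3 to 37.7°C among different individuals", and also in one patient over 24 hours. The definitions section sets peripheral fever at 37.5°C or above and peripheral hypothermia below 34.2°C.

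**The concern.** A percentage is a poor measure of discordance for body temperature in °C, because the zero of the scale lies far from any value a patient can have. A difference of 15% sounds moderate but is more than five degrees. Two readings taken together, one hypothermic and one febrile by the protocol's own cut-offs, would count as agreeing.

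The remaining steps do not help. Restricting the mean to the three closest readings happens only after the 15% trigger, and the fifth-reading step only after a fourth reading. A discordant reading below the trigger therefore stays in the axillary mean, and its error enters the primary ICC as if it were disagreement by the camera. A repeat that was not taken at the bedside cannot be obtained afterwards, so a later analysis plan cannot fully repair this.

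**Working it through.** **Sample size, for context.** Bonett's precision formula with 2 measurements, ICC r = 0.80 and full width w = 0.10 gives n = 8 × 1.96² × (1 − r)² × (1 + r)² / (2 × w²) + 1 = 200.1, rounded up to 201. Allowing for 10% loss, 201 / 0.9 rounds up to 224, the protocol's figure. The sample size is not in question here.

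**The trigger in °C.**
- At the hypothermia cut-off: 0.15 × 34.2 = 5.13°C
- At the normal value: 0.15 × 36.7 = 5.51°C
- At the fever cut-off: 0.15 × 37.5 = 5.63°C

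**The protocol's own ranges as percentages** (larger figure with the lower value as base, smaller with the higher value).
- Normal range: 37.7 − 35.3 = 2.4°C; 2.4 / 35.3 = 6.8% and 2.4 / 37.7 = 6.4%
- Gap between cut-offs: 37.5 − 34.2 = 3.3°C; 3.3 / 34.2 = 9.6% and 3.3 / 37.5 = 8.8%

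Both are well under 15% whichever base is used.

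**How far one reading can move the mean without a repeat.** Take two readings at 36.7°C and let x be the lowest third reading that does not trigger. The shift is (36.7 − x) / 3.

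| Base of the percentage | x (°C) | Shift of the mean (°C) |
|---|---|---|
| Minimum | 36.7 / 1.15 = 31.91 | 1.60 |
| Midpoint | 36.7 × 0.925 / 1.075 = 31.58 | 1.71 |
| Maximum | 36.7 × 0.85 = 31.20 | 1.84 |

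**An example.** Readings of 37.6, 37.7 and 34.1°C differ by 3.6 / 37.7 = 9.5% to 3.6 / 34.1 = 10.6%. No fourth reading is taken. The mean is 36.47°C, against 37.65°C for the two concordant readings, a difference of 1.18°C.

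**How often the rule would fire.** The protocol gives no within-triplet standard deviation (SD), so this is illustrative. In 4,000,000 simulated triplets with normal errors around 36.7°C:
- SD 0.75°C: trigger probability at most 4.5 × 10⁻⁶, or 0.001 expected triggers in 224 triplets.
- SD 1.0°C: probability 9.0 × 10⁻⁴ (minimum as base), 3.1 × 10⁻⁴ (mean) or 8.4 × 10⁻⁵ (maximum), or 0.20, 0.07 and 0.02 expected triggers in 224.

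**Sensitivity of the ICC.** Assumptions: absolute-agreement, single-measure ICC; true value 0.80 with equal error variance of 0.25 × sT² in each method, where sT is the SD between records; a fraction f of triplets with one reading d too low, so the mean is low by s = d / 3. Then

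ICC = sT² / (sT² + [2 × 0.25 × sT² + s² f(1 − f)] / 2 + (s f)² / 2),

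which simplifies to sT² / (1.25 sT² + s² f / 2).

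With d = 3°C (8.9% when the other readings are 36.7°C, so no trigger), s = 1.0°C. The value sT = 0.6°C is a quarter of the normal range (2.4 / 4); 1.0°C is a wider alternative.

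| f | ICC, sT = 0.6°C | Loss | ICC, sT = 1.0°C | Loss |
|---|---|---|---|---|
| 2% | 0.36 / 0.460 = 0.783 | 0.017 | 1 / 1.260 = 0.794 | 0.006 |
| 5% | 0.36 / 0.475 = 0.758 | 0.042 | 1 / 1.275 = 0.784 | 0.016 |
| 10% | 0.36 / 0.500 = 0.720 | 0.080 | 1 / 1.300 = 0.769 | 0.031 |

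A simulation of 1,000,000 records agrees within 0.001. With smaller errors the effect nearly vanishes: for d = 1°C and sT = 0.8°C, a separate simulation gives 0.797 at f = 5% and 0.795 at f = 10%.

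**The case against.** The strongest reply is that nothing shows harm. If repeat axillary readings agree within a few tenths of a degree, a rule that never fires costs nothing, because the mean of three readings already damps noise of that size. Harm needs isolated errors of several degrees, and the protocol does not suggest how often these occur. The contamination rates above are assumed, with all errors in one direction. Only one of the six scenarios loses more than 0.05, and it pairs the highest rate with the smaller SD. The background says about half of critical patients reach the fever level, so the wider spread is the more plausible one, and there the worst loss is 0.031. The planned ±0.05 is sampling precision and not a tolerance for bias. All of this stands, and it limits what can be claimed about the ICC.

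It can also be said that the rule was meant only to catch gross failure such as a displaced probe, and for that it works. The protocol states no purpose. On that reading, though, nothing guards the comparator against any error smaller than about five degrees.

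Finally, if the individual readings are kept, outliers can be seen and a sensitivity analysis run. That is fair, since the protocol does not say they are discarded. It does not say they are stored either, and with only three readings there is no fourth to settle which one was wrong.

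**Conclusion.** The point holds. That the 15% trigger is too wide follows from the protocol's own figures and needs no assumption. It is 5.1 to 5.6°C between the two cut-offs, more than the whole normal range and more than the distance from hypothermia to fever. No other tolerance is given. Short of gross probe failure, the check on the primary comparator will practically never act.

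The size of the consequence is uncertain. A single reading can move the axillary mean by up to 1.60 to 1.84°C without a repeat. For a reading 3°C low in 2 to 10% of triplets, the loss in the ICC runs from 0.006 to 0.080; for errors near 1°C it is negligible. These figures are a sensitivity range resting on assumed rates and SDs, not an estimate. Fever and hypothermia status could be affected as well, but only if they are taken from this mean, which the protocol does not say. The rule should be corrected; the design and sample size are not at risk.

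**What to change.** Replace the percentage with an absolute tolerance in °C, justified by the stated accuracy and repeatability of the axillary thermometer used. Apply the same tolerance to define when readings are different and when they are similar. Store every individual reading. Keeping the mean of the three closest readings is reasonable.

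Two secondary clarifications belong in the same edit: a maximum number of repeats, with the handling of a time point that reaches it; and whether fever and hypothermia status use this mean or a single reading.

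The cost is one or two sentences in the protocol, one database field per reading and some extra axillary readings, since the repeat procedure already exists. The tighter the tolerance, the more repeats. Under assumed within-triplet SDs of 0.1, 0.2 and 0.3°C, a range above 0.5°C occurs in about 0.1%, 18% and 47% of triplets, and a range above 1.0°C in about 0%, 0.1% and 5%. These are illustrations of workload and not proposed limits.
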